8.1 Safety Endpoints

Safety will be assessed based on AEs, SAEs, treatment discontinuations due to AEs, DLTs, measurements of cytokines in serum, periodic 12-lead ECG recordings, physical examinations, vital signs measurements, ECOG performance status, and hematology, coagulation panel, biochemistry, pregnancy testing (for women of child-bearing potential) and urinalysis test results.

8.2 Endpoints

8.2.1 Primary Endpoints

The primary objectives for Part 1 (dose-escalation) and Part 2 (expansion) of the study are:

- Assessment of DLTs (Section 7.3.1.1) and determination of the MTD (Section 4.1.1) for ADCT-301 during Part 1.
- Determination of the recommended dose of ADCT-301 for Part 2 by the DESC.
- Assessment of safety parameters in Parts 1 and Part 2 (Section 8.6.1), schedule of safety assessments in the Schedule of Procedures for the Q3W and QW dosing schedules in Table 1 and Table 3, respectively (Appendix 13.1).

8.2.2 Secondary Endpoints

The following secondary endpoints will be determined in Part 1 and Part 2:

- Determination of DOR, ORR, OS, and PFS (Section 8.6.2).
- Determination of PK parameters (Section 7.2) for ADCT-301 (total antibody; $DAR \geq 0$), PBD-conjugated antibody ($DAR \geq 1$), and free warhead SG3199.
- Measurement of ADAs to ADCT-301 before, during, and after treatment with ADCT-301 (Section 8.6.3).

[REDACTED]

[REDACTED]

8.3 Sample Size Calculations

This is a Phase 1 study with a maximum total sample size of 80 patients. It is expected that Part 1 will enroll up to 50 patients, and Part 2 will enroll up to 30 patients.

Patients will be enrolled in Part 2 of the study in cohorts of approximately 10. The cohorts will be enrolled at the dose level recommended in Part 1.

The DESC will make recommendations with regard to the intended differences between these cohorts, e.g. tumor subtypes, dosing regimen or dose levels, as well as the number of these cohorts, taking into account the limit on the overall number of patients as specified above and safety/efficacy data observed up to that decision point.

8.4 Analysis Sets

Six analysis sets will be used in this study:

- The Safety analysis set will consist of all patients who receive study drug.
- The DLT-evaluable analysis set will consist of all patients in Part 1 who receive study drug and excludes patients who discontinue from the study during the first 21-day cycle without experiencing a DLT.
- The Efficacy analysis set will consist of all patients with valid baseline data who receive at least 2 doses of study drug, or who have documented progression of disease at any time after the first dose of study drug.
- The PK analysis set will consist of all patients who receive study drug and have sufficient concentration data for PK analysis.
- The PD analysis set will consist of all patients who receive study drug and have sufficient data available for analysis.

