4.1.1 Dose-escalation (Part 1) and Determination of Maximum Tolerated Dose

Dose-escalation will be conducted according to a 3+3 design (Figure 2). The initial dose of ADCT-301 will be 3 µg/kg (Dose Level 1), and the highest allowed dose will be 150 µg/kg every three weeks (50 µg/kg every week).

The DLT (see Section 7.3.1.1 for further details) observation period for dose-escalation will be 1 cycle. The first patient at each new dose level must be observed for 7 days for occurrence of AEs prior to treating the second patient at that dose level. Patients will be entered sequentially to each dose level.

For each dose level, if none of the first 3 patients at that level experiences a DLT, new patients may be entered at the next higher dose level. If 1 of 3 patients experiences a DLT, up to 3 more patients are to be treated at that same dose level. If none of the additional 3 patients at that dose level experiences a DLT, new patients may then be entered at the next higher dose level. However, if 1 or more of the additional 3 patients experiences a DLT, then no further patients are to be started at that dose level and the preceding dose is identified as the MTD. The MTD, therefore, is defined as the highest dose level at which none of the first 3 treated patients, or no more than 1 of the first 6 treated patients, experiences a DLT.

No intra-patient dose-escalation is allowed.

[figure not shown]

Figure 2. Schematic Representation for Dose-escalation (3+3) Design

* For every 3 weeks (Q3W) administration, the dose increase will never exceed 100% or 20 µg/kg at dose levels below 100 µg/kg and 50 µg/kg for dose levels between 100 and 150 µg/kg, whichever is less. Dose adjustment for other treatment schedules, such as QW dosing are included below. Abbreviations: DLT, dose-limiting toxicity; MTD, maximum tolerated dose; <, less than; ≥ greater than or equal to.

The number of dose levels will depend on the emergent toxicity profile of ADCT-301 and will be decided by the DESC ([Section 7.3.1.2](#)); PK and PD evaluations may also inform decision making.

During Part 1 (dose-escalation), the DESC may expand enrollment at doses below the current dose level as part of the dose-escalation process. Additional patients may only be added at a lower dose level provided there is at least 1 patient who has achieved a PR or better ([Section 7.1](#)).

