No more than 9 additional patients (e.g., 3 cohorts of 3 patients) will be enrolled in the remaining dose escalation portion of this study (max. dose level 50 µg/kg/week) from the date of protocol amendment number 5, unless 2 additional patients attain a PR, CR, or CRi, in which case additional patients will be treated at a dose patients have cleared the DLT period, to determine if there is sufficient evidence of clinical activity to continue the study.

No more than 10 patients in total can be treated at any dose level unless ≥ 3 of the 10 patients have achieved a PR or better.

Every 3-Week Administration

Patients will be given ADCT-301 on Day 1 of each 3-week treatment cycle.

When the dose is escalated, the dose may increase by 100% if no DLTs are observed at the current level (e.g., at 6 µg/kg, the dose increase is 6 µg/kg). Once a DLT is observed at a given dose level, the next dose may only increase by 50% (e.g., at 6 µg/kg, the dose increase is 3 µg/kg). The dose may never increase by more than 100%, or more than an absolute value of 20 µg/kg at dose levels below 100 µg/kg and 50 µg/kg for dose levels between 100 and 150 µg/kg, whichever is less.

Weekly Administration

Patients will be given ADCT-301 (QW) on Days 1, 8, and 15 of each 3-week treatment cycle.

The first dose level for the QW dosing will be based on the safety and tolerability of patients who have been treated on the Q3W schedule. The first 3 patients will be given a cumulative dose each cycle that is comparable to (but not higher than) the highest dose tested at the Q3W dose schedule at which 3 patients completed the DLT observation period without a DLT. For example, if the highest Q3W dose tested at which 3 patients did not experience a DLT was cohort 92 µg/kg, the first cohort to receive (QW) dosing will receive 30 µg/kg each week for 3 weeks.

When the dose is escalated, the dose may increase by 50% if no DLTs are observed at the current level. Once a DLT is observed at a given dose level, the next dose may only increase by 25%. The dose may never increase by more than 50%, or more than an absolute value of 20 µg/kg/week, whichever is less.

A patient will maintain the same treatment schedule throughout the duration of the trial.

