5.2.3 Patient Replacements

Any patient in Part 1 who discontinues before completion of the first treatment cycle, for any reason other than a DLT, is to be replaced.

6 Study Treatments

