6.4 Dose Delays and Modifications

Patients will receive the first 2 cycles, irrespective of blood count recovery. For patients achieving a CR/CRi, the subsequent cycle would be delayed until peripheral blood count recovery (absolute neutrophil count [ANC] $>0.5 \times 10^9/L$ and/or platelets $>50 \times 10^9/L$).

The Investigator should suspend ADCT-301 dosing for up to 21 days for any patient who experiences a protocol-defined DLT during any treatment cycle. At the discretion of the Investigator, the dose may also be delayed for up to 21 days for any toxicity that does not meet DLT criteria. Resumption of dosing with ADCT-301 after suspension is at the discretion of the Investigator, based on assessment of the patient's clinical condition and whether or not the patient is deriving potential clinical benefit from treatment with ADCT-301. Following recovery to CTCAE Grade 1 or to baseline grade, treatment with ADCT-301 may resume at the Investigator's discretion.

Patients who resume treatment following a dose delay may, at the discretion of the Investigator, have their dose reduced by 1 dose level. If toxicity recurs at a severity that would mandate a dose delay, then the dose may be further reduced 1 dose level. If toxicity recurs at such level, then the patient is to be discontinued from treatment. Dose re-escalation is allowed at the Investigator's discretion, at maximum to the dose level the patient was initially assigned to.

Dosing frequency may be adjusted according to individual patient response as described in [Section 4.1.1](#).

Patients experiencing certain types of infection during the course of participation in this clinical study also must delay further dosing, as stipulated in [Section 7.3.4.5](#).

Patients experiencing any autoimmune toxicities (e.g., endocrinopathies) \geq grade 1 need to be followed at least weekly to quickly detect deterioration and modify dosing as per DLT criteria (can be done by telephone unless symptoms worsen).

Patients who experience a DLT ([Section 7.3.1.1](#)) during Cycle 1 are to be permanently withdrawn from the study. Patients who experience the following significant toxicities will be immediately and permanently withdrawn from treatment with ADCT-301:

- Any patient who experiences a CTCAE Grade 3 or higher hypersensitivity reaction, regardless of premedication, during any cycle of treatment ([Appendix 13.2](#)).

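### On weekly dosing no minimum Cycle 1 exposure is needed to count as DLT-free, so a patient whose Day 8 and Day 15 infusions are held can help clear a dose level after a third of the cycle dose

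*Protocol*

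**What the plan says.** **Who is evaluable.** Protocol 8.4 starts the DLT-evaluable set from "all patients in Part 1 who receive study drug" and then "excludes patients who discontinue from the study during the first 21-day cycle without experiencing a DLT". It names no number of infusions and no share of the planned dose. In the same list, the Efficacy set does carry an exposure condition: two doses, or documented progression.

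**How a level is cleared.** Protocol 4.1.1 says the DLT "observation period for dose-escalation will be 1 cycle", and "if none of the first 3 patients at that level experiences a DLT, new patients may be entered at the next higher dose level". One DLT in three leads to up to three more patients, and the level is cleared if none of those has a DLT. Exposure is not mentioned.

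**Weekly schedule.** "Patients will be given ADCT-301 (QW) on Days 1, 8, and 15 of each 3-week treatment cycle". The first weekly level is matched to the every-3-week schedule on cumulative dose per cycle.

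**How infusions come to be held.**
- Under 6.4, "the dose may also be delayed for up to 21 days for any toxicity that does not meet DLT criteria".
- Also under 6.4, dosing must wait while a possible early sign of polyradiculopathy/GBS is investigated.
- Under 7.3.4.5, a confirmed infection with a listed pathogen requires at least four weeks between symptom resolution and the next dose.
- The 6.4 limit of more than 21 days, which leads to withdrawal from treatment, is counted from the planned Day 1 dose.

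**Replacement.** Protocol 5.2.3: "Any patient in Part 1 who discontinues before completion of the first treatment cycle, for any reason other than a DLT, is to be replaced". Missed infusions are not a trigger.

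**SAP.** Section 4.1 defines only the Safety set, and DLTs are listed (4.8.1). Section 4.7.1 tabulates the number of infusions and lists infusion details. Nothing links either to evaluability.

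**The concern.** With one infusion per cycle, a patient who has received any drug has normally received the whole Cycle 1 dose, so a rule based only on staying in the study is adequate. On the weekly schedule the same rule lets a patient with one infusion of three stand as evidence on the full level.

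The error runs one way. An under-dosed patient without a DLT lowers the apparent DLT rate of the assigned level, and with three to six patients deciding each level, one or two such patients matter. The reasons for holding a dose include toxicity below the DLT threshold. Peripheral neuropathy of Grade 2 or more is a DLT (7.3.1.1), while a suspicious new Grade 1 neurological finding leads to a hold (6.4). A patient held on an early signal may not receive the remaining Cycle 1 exposure inside the window, yet is counted as DLT-free.

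**Working it through.** **1. Dose arithmetic, reproducing the protocol's figures.** The stated maximum is 150 µg/kg every three weeks, or 50 µg/kg weekly: 3 × 50 = 150. The worked example pairs a 92 µg/kg cohort with 30 µg/kg weekly: 3 × 30 = 90, not above 92. Both agree. Day 1 alone is 30/90 = 50/150 = one third of the cycle dose. The documents give no operating characteristics for the 3+3 rule, so there is no further figure to reproduce.

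**2. Following one patient through the rules.** Take a weekly patient given Day 1, with Days 8 and 15 held, no DLT and no discontinuation.
- 8.4: received drug and did not leave the study, so evaluable.
- 4.1.1: counted as DLT-free at the assigned level.
- 5.2.3: did not discontinue, so not replaced.
- 6.4: losing Days 8 and 15 does not by itself reach the 21-day limit.

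The infection rule alone can remove both infusions. If symptoms resolve on Day 1 or later, the next dose falls on Day 29 or later (1 + 28), after Day 15.

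**3. Illustrative size.** Assumptions, none from the documents: DLT risk 0.40 with three infusions and 0.15 with one; a share s of patients receives Day 1 only, independently of their own risk.

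For the first three patients, with m of them under-dosed, P(0/3) = 0.60^(3−m) × 0.85^m, which is 0.216, 0.306 and 0.433 for m = 0, 1, 2.

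For the whole rule, the mixed risk is p = 0.40 − 0.25s, and P(clear) = (1−p)³ + 3p(1−p)⁵.

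| Share with Day 1 only | p | P(clear) |
|---|---|---|
| 0 | 0.400 | 0.309 |
| 5% | 0.3875 | 0.330 |
| 10% | 0.375 | 0.351 |
| 20% | 0.350 | 0.396 |
| 33% | 0.317 | 0.461 |

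**4. Sensitivity.** With risks of 0.30 and 0.10 and a third under-dosed, p falls from 0.30 to 0.233 and P(clear) rises from 0.494 to 0.636. A second model takes equal, independent risk per infusion, so the one-infusion risk is 1 − (1 − 0.40)^(1/3) = 0.157. With exactly one patient in each group of three under-dosed, P(clear) goes from 0.309 to 0.444. The direction is the same and the size similar.

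**5. Whether the SAP would show it.** Relative dose intensity (4.7.1) for a weekly patient whose only infusion is Day 1 is [dose ÷ (1/7 + 6/7)] ÷ dose = 100%. If Cycle 2 Day 1 is then given on Day 22, it is [2 × dose ÷ (22/7 + 6/7)] ÷ dose = 50%. The summary can therefore miss the case, although the infusion listing would contain it.

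**The case against.** **Replacement may already cover part of this.** A reader might infer that anyone who gets only Day 1 and stays in the study escapes replacement. The text does not support that. Section 8.4 speaks of leaving *the study*, but 5.2.3 says only that the patient *discontinues*, which can include stopping treatment. A patient who stops after Day 1 and stays in follow-up may be replaced under 5.2.3 and still counted under 8.4. The clear gap is the patient whose infusions are held while treatment is meant to continue; the difference in wording is a second, smaller one.

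**Delayed is not the same as missed.** The documents do not say whether a late Day 8 or Day 15 infusion is given later or dropped, nor whether the DLT window moves with it. This stands: they are silent. Section 8.4 does tie evaluability to the first 21 days.

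**Frequency is unknown.** A reader might infer that doses are often held for sub-DLT toxicity. Nothing in the documents shows this. The first two cycles are given whatever the blood counts (6.4), and many Grade 3 or higher non-hematologic events are themselves DLTs (7.3.1.1). What remains is mainly lower-grade toxicity, neurological work-up and listed infections. At a 5% to 10% share the effect is two to four percentage points.

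**The DESC can use judgment.** Escalation is permitted, not automatic, and the DESC sets dose levels from safety findings (7.3.1.2). That is real protection, but no rule obliges it to set such a patient aside.

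**The trial has ended.** SAP 3.3 says it stopped before dose escalation was complete. A reader might infer that a cohort was wrongly cleared or that a final MTD is biased; the documents show neither. The point bears on how the Part 1 escalation decisions are read.

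**Conclusion.** The gap is real and should be closed. Followed as written, 8.4 and 4.1.1 count a weekly patient with held infusions, no DLT and no discontinuation as DLT-free at the full level after as little as one third of the Cycle 1 dose. That rests on the text alone.

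The size does not. On assumed risks of 40% and 15%, the chance of clearing a level rises by 2 to 15 percentage points as the share with Day 1 only goes from 5% to 33%. Neither the risks nor the shares come from the documents, and the calculation treats under-dosing as unrelated to a patient's own risk. It shows direction and plausible scale; it does not estimate what happened in this trial.

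**What to change.** Use one definition, in the same words, in 8.4 and 5.2.3:
- A Part 1 patient without a DLT is evaluable only if all planned Cycle 1 infusions were given, or a single numerical minimum share of the planned Cycle 1 dose fixed in advance, and the patient was observed through Day 21. Otherwise the patient is replaced for the 3+3 count.
- A patient with a DLT in Cycle 1 is always evaluable.
- State whether replacements count toward the limit of 9 additional patients in 4.1.1.

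In the SAP, show the Cycle 1 infusions received by each patient in the DLT listing. With the trial closed, this is the part that still helps: it lets a reader see what exposure each Part 1 decision rested on. The data are already collected for the exposure listing.

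**Cost.** An occasional extra patient, and some conservatism. Counting every DLT while replacing under-dosed patients without one raises the evaluable DLT rate. In the one-third scenario it is 0.317 ÷ (2/3 + 1/3 × 0.15) = 0.317 ÷ 0.717 = 0.442, so P(clear) is 0.246, against 0.309 with full dosing. At a 10% share it is 0.375 ÷ 0.915 = 0.410, giving 0.294. The rule therefore does not restore 0.309 exactly; it errs on the cautious side, and by little when few doses are held.

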8.5 Description of Subgroups to be Analyzed

Subgroup analyses, if planned, will be described in the SAP.

8.6 Statistical Analysis Methodology

8.6.1 Safety Analyses

8.6.1.1 Analyses of Adverse Events

An AE will be considered to be a TEAE if it begins or worsens on or after the patient's first study medication dose date and before the last dose date up to 84 days (12 weeks).

Planned summaries of TEAEs will be detailed in the SAP and will include:

- All TEAEs.
- All serious TEAEs.
- All treatment-related TEAEs.
- All treatment-related serious TEAEs.
- All TEAEs resulting in study drug discontinuation.
- All DLTs.

Other AE analyses of interest will be specified in the SAP.

The incidence of deaths and the primary cause of death will be summarized.

8.6.1.2 Clinical Laboratory Results

Clinical hematology, biochemistry, coagulation panel, and urinalysis data will be summarized at each scheduled assessment. Numeric hematology and biochemistry results will be summarized using change from baseline. All results will be summarized using shift from baseline. Shifts for clinical laboratory results that can be graded according to CTCAE Version 4.0 will be summarized by CTCAE grade. Shifts for other numeric laboratory results will be by high/normal/low flag. Shifts for all other laboratory results will be by normal/abnormal flag.

Summaries by visit will include data from scheduled assessments, and all data will be reported according to the nominal visit date for which it was recorded. Unscheduled data will be included in "worst case post-baseline" summaries, which will capture a worst case across all scheduled and unscheduled visits after the first dose of study treatment. Further details will be provided in the SAP.

8.6.1.3 Additional Safety Assessments

The results of scheduled assessments of cytokine levels, vital signs, physical examinations, ECOG performance status, and 12-lead ECGs will be summarized. All data will be reported according to the nominal visit date for which it was recorded (i.e., no visit windows will be applied). Unscheduled data will be included in "worst case" summaries, which will capture a worst case across all scheduled and unscheduled visits after the first dose of study treatment. All data will be listed. Further details will be provided in the SAP.

8.6.2 Efficacy Analysis

Determination of DOR and ORR will be based on the Investigator's evaluation of the patient's response to ADCT-301 (Section 7.1). Overall survival and PFS will also be determined.

8.6.2.1 Duration of Response

Duration of response will be defined among responders (CR, CRi, or PR) as the time from the earliest date of first response until the first date of either disease progression or death due to any cause. The date of disease progression is defined for patients with CR or CRi as the first date of reappearance of blast cells in bone marrow and/or peripheral blood to a level $\geq 5\%$, or development of extramedullary disease. In patients with PR, it is defined as the first date of an increase in blast cells in bone marrow and/or peripheral blood such that the patient does not continue to meet the criteria for PR (Section 7.1). For patients whose disease has not progressed or who have not died at the time of the analysis, censoring will be performed using the date of the last disease assessment. In addition, patients with disease progression or who have died after an extended loss to follow-up by the investigative site will be censored at the date of the last disease assessment prior to the extended loss to follow-up. Further details on censoring rules will be outlined in the SAP.

8.6.2.2 Overall Response Rate

The ORR is defined as the proportion of patients with a best overall response of CR, CRi, or PR at the time each patient discontinues treatment with ADCT-301.

8.6.2.3 Overall Survival

Overall survival is defined as the time from the first dose of study drug treatment until the date of death due to any cause. For patients who have not died at the time of the analysis, censoring will be performed using the date the patient was last known to be alive. Further details on censoring rules will be outlined in the SAP.

8.6.2.4 Progression-Free Survival

Progression-free survival is defined as the time from first dose of study drug until the first date of either disease progression or death due to any cause. The date of disease progression is defined for patients with CR or CRi as the first date of reappearance of blast cells in bone marrow and/or peripheral blood to a level $\geq 5\%$, or development of extramedullary disease. In patients with PR, PFS is defined as the first date of an increase in blast cells in bone marrow and/or peripheral blood such that the patient does not continue to meet the criteria for PR (Section 7.1).

Patients without disease progression or patients who died after an extended loss to follow-up will be censored at the date of the last adequate disease assessment prior to the extended loss to follow-up. Further details on censoring rules will be outlined in the SAP.

[REDACTED]

